## 6.2. Exclusion Criteria

Subjects will be excluded from study enrollment if they meet any of the following criteria at screening and/or enrollment:

- [8] are investigative site personnel directly affiliated with this study and their immediate families. Immediate family is defined as a spouse, biological or legal guardian, child, or sibling.
- [9] are Lilly employees or employees of Covance
- [10] are currently enrolled in a clinical study involving an investigational product or any other type of medical research judged not to be scientifically or medically compatible with this study
- [11] have participated in a clinical trial involving an investigational product within 30 days or 5 half-lives (whichever is longer) prior to screening. If the clinical trial involved treatment with biologic agents (such as monoclonal antibodies, including marketed drugs), at least 3 months or 5 half-lives (whichever is longer) should have elapsed prior to Day 1
- [12] have previously completed or withdrawn from this study or any other study investigating LY3074828, and have previously received the investigational product
- [13] have known allergies to LY3074828, related compounds or any components of the formulation, or history of significant atopy
- [14] have an abnormality in the 12-lead ECG that, in the opinion of the investigator, increases the risks associated with participating in the study
- [15] have an abnormal blood pressure as determined by the investigator
- [16] have a history or presence of cardiovascular, respiratory, hepatic, renal, gastrointestinal, endocrine, hematological (including thalassemia and serious glucose-6-phosphate dehydrogenase deficiency), or neurological disorders capable of significantly altering the absorption, metabolism, or elimination of drugs; of constituting a risk when taking the investigational product; or of interfering with the interpretation of data
- [17] have known or ongoing psychiatric disorders deemed clinically significant by the investigator

- [18] regularly use known drugs of abuse and/or show positive findings on drug screening
- [19] show evidence of HIV infection and/or positive human HIV antibodies
- [20] show evidence of hepatitis C and/or positive hepatitis C antibody
- [21] show evidence of hepatitis B, and/or positive hepatitis B surface antigen, and/or hepatitis B core antibody
- [22] are women who are lactating
- [23] have used or intend to use over-the-counter or prescription medications, including herbal medications, within 14 days prior to dosing and for the duration of the study. Stable doses of oral contraceptive or hormone-replacement therapy are permitted, at the discretion of the investigator
- [24] have donated blood of more than 500 mL within the month prior to screening
- [25] have an average weekly alcohol intake that exceeds 21 units per week (males) and 14 units per week (females), have a positive test for ethanol, or are unwilling to abide by the alcohol restrictions described in Section 6.3.2 (1 unit = 12 oz or 360 mL of beer; 5 oz or 150 mL of wine; 1.5 oz or 45 mL of distilled spirits)
- [26] have a tobacco consumption of more than 10 cigarettes per day (or equivalent), are unwilling to refrain from smoking for approximately 1 hour prior to each ECG and vital sign measurements during the study, or who are unwilling to abide by the CRU smoking guidelines described in Section 6.3.2
- [27] have had symptomatic herpes zoster within 3 months of screening
- [28] show evidence of active or latent TB, as documented by medical history, examination, and TB testing (negative [not indeterminate] QuantiFERON®-TB Gold test); or have had household contact with a person with active TB, unless appropriate and documented prophylaxis treatment has been given
- [29] have received live vaccine(s), including attenuated live vaccines, and those administered intranasally, within 8 weeks of screening, or intend to during the study
- [30] have been treated with steroids within 1 month of screening, or intend to during the study
- [31] are immunocompromised
- [32] have received treatment with biologic agents (such as monoclonal antibodies) for a medical condition within 3 months or 5 half-lives (whichever is longer) prior to Day 1
- [33] have significant allergies to humanized monoclonal antibodies

- [34] have clinically significant multiple or severe drug allergies, or intolerance to topical corticosteroids, or severe post treatment hypersensitivity reactions (including, but not limited to, erythema multiforme major, linear immunoglobulin A dermatosis, toxic epidermal necrolysis, or exfoliative dermatitis)
- [35] have had lymphoma, leukemia, or any malignancy within the past 5 years except for basal cell or squamous epithelial carcinomas of the skin that have been resected with no evidence of metastatic disease for 3 years
- [36] have had breast cancer within the past 10 years
- [37] in the opinion of the investigator or sponsor, are unsuitable for inclusion in the study

### **6.3. Lifestyle and/or Dietary Requirements**

Throughout the study, subjects may undergo medical assessments and review of compliance with requirements before continuing in the study.

#### **6.3.1. Meals and Dietary Restrictions**

Subjects should fast overnight for at least 8 hours before dosing (water is permitted). Standard meals will be provided at all other times while subjects are resident at the CRU, as per the CRU's policy.

#### **6.3.2. Caffeine, Alcohol, and Tobacco**

Subjects should not consume caffeine while at the CRU, and for 12 hours prior to admission to the CRU. At other times during the outpatient period, subjects will be allowed to maintain their regular caffeine consumption.

Alcohol consumption is not permitted while at the CRU, and for 12 hours prior to each study visit. At other times, alcohol consumption should be limited to 2 units per day (1 unit = 12 oz or 360 mL of beer; 5 oz or 150 mL of wine; 1.5 oz or 45 mL of distilled spirits).

Subjects who smoke will be advised to not increase their consumption of tobacco products during the study. Subjects will be asked to refrain from smoking for approximately 1 hour prior to each ECG and vital sign measurements, and to abide by the CRU smoking guidelines.

#### **6.3.3. Activity**

Subjects will be advised to maintain their regular levels of physical activity/exercise during the study, but to refrain from vigorous exercise. Strenuous activity should be avoided from 24 hours prior to admission until discharge from the CRU. While certain study procedures are in progress at the site, subjects may be required to remain recumbent or sitting.

### **6.4. Screen Failures**

Individuals who do not meet the criteria for participation in this study (screen failure) may not be re-screened.

## 7. Treatment

### 7.1. Treatment Administered

The LY3074828 lyophilized formulation will be supplied in a sterile vial to be reconstituted prior to injection as detailed in the pharmacy instructions.

The LY3074828 solution formulations will be supplied in CCI [REDACTED] containing CCI [REDACTED] LY3074828. The CCI [REDACTED] dose will comprise two CCI [REDACTED] and the CCI [REDACTED] CCI [REDACTED]

The actual date and time of all dose preparation and administration will be documented, and drug accountability records will be maintained by the site pharmacy.

This study involves a comparison of CCI [REDACTED] SC doses of LY3074828 that will be prepared from a lyophilized product with CCI [REDACTED] and CCI [REDACTED] SC doses of LY3074828 that will be supplied as a solution in PFSs. [Table AMAE.2](#) shows the treatment regimens.

**Table AMAE.2. Treatments Administered**

Treatment arm	Lyophilized formulation CCI [REDACTED]	Pre-filled syringes CCI [REDACTED]	Pre-filled syringes CCI [REDACTED]
Reference/test	Reference	Test 1	Test 2
Product	LY3074828	LY3074828	LY3074828
Dose	CCI [REDACTED] a	CCI [REDACTED]	CCI [REDACTED]
Concentration	CCI [REDACTED]	CCI [REDACTED]	CCI [REDACTED]
Injection volumes	CCI [REDACTED] CCI [REDACTED] CCI [REDACTED]	CCI [REDACTED] CCI [REDACTED]	CCI [REDACTED] CCI [REDACTED]
Number of injections	3	2	4
Formulation and presentation	Lyophilized powder for reconstitution	Solution in a PFS	Solution in a PFS

Abbreviations: PFS = pre-filled syringe.

a Theoretical total dose = 252 mg

Injection-sites selected for SC administration should be in the abdominal region approximately 5 cm from the umbilicus, and treatment should be administered with the needle applied at approximately 45 degrees with pinching the skin. Subcutaneous administration of LY3074828 should be given by a limited number of individuals for consistency. The same type of syringe and needle (27-gauge, half-inch needle) should be used for all subjects to ensure all injections are delivered to a consistent depth target into the SC space. Subsequent injection(s) should be given immediately following the previous injection.

For the lyophilized formulation (Reference), the [CC1] injection and the first of the [CC1] injections will be given into lower quadrants of the abdomen. The remaining [CC1] injection will be administered into an upper quadrant. The order and location of the first 2 injections will be randomized (see Section 7.2).

For administration of the [CC1] solution formulation in PFSs (Test 1), injections will be given into separate lower quadrants of the abdomen. For administration of the [CC1] solution formulation in PFSs (Test 2), the first 2 injections will be given into separate lower quadrants of the abdomen, and the final 2 injections will be given into separate upper quadrants of the abdomen.

Further information around SC administration will be in pharmacy handling instructions.

Investigational products will be prepared at the site by pharmacists or other trained personnel. Investigational products will only be administered to subjects on-site by nurses or other appropriately trained personnel.

The investigator or designee is responsible for:

- explaining the correct use of the investigational products to the site personnel
- verifying that instructions are followed properly
- maintaining accurate records of investigational product dispensing and collection
- returning all unused medication to Lilly or its designee at the end of the study

Note: In some cases, the site may destroy the material if, during the investigative site selection, the evaluator has verified and documented that the site has appropriate facilities and written procedures to dispose of clinical trial materials.

### 7.1.1. Packaging and Labeling

LY3074828 lyophilized formulation and solution formulation in PFSs will be supplied to the investigator by Lilly. Clinical trial materials are manufactured in accordance with good manufacturing practices. All investigational products will be stored, inventoried, reconciled, and destroyed according to applicable regulations.

LY3074828 lyophilized formulation will be supplied for clinical trial use as a powder in a glass vial and should be stored refrigerated (2°C to 8°C). Each vial is manufactured to deliver [CC1] LY3074828 and will be reconstituted with sterile water to a concentration of [CC1]. Contents from multiple vials will be pooled for each injection, as required.

LY3074828 solution formulation will be supplied as an injectable solution in a 1-mL, single-dose, disposable manual syringe. Each syringe of LY3074828 will be designed to deliver [CC1] LY3074828 and therefore two or four PFSs will be required to administer doses of [CC1] LY3074828 or [CC1] LY3074828, respectively. The PFSs should be stored refrigerated, and should be removed from refrigerated storage and allowed to equilibrate to room temperature for approximately 30 minutes prior to dose administration.

Clinical trial materials will be labeled according to the country's regulatory requirements.

## 7.2. Method of Treatment Assignment

Subjects will be randomized to 1 of 3 treatment arms (CC1 LY3074828 lyophilized formulation [Reference], CC1 LY3074828 solution formulation [Test 1], or 500 mg LY3074828 solution formulation [Test 2]). Those that are randomized to receive the lyophilized formulation will be further randomized to 1 of 4 treatment sequences:

Sequence	First Injection	Second Injection
1	CC1 administered into left lower quadrant	CC1 administered into right lower quadrant
2	CC1 administered into right lower quadrant	CC1 administered into left lower quadrant
3	CC1 administered into left lower quadrant	CC1 administered into right lower quadrant
4	CC1 administered into right lower quadrant	CC1 administered into left lower quadrant

For all sequences, the third injection will comprise a 1.0 mL injection administered into an upper quadrant.

Randomization will be performed using a computer-generated randomization schedule.

### 7.2.1. Selection and Timing of Doses

The actual time of all dose administrations will be recorded in the subject's electronic case report form (eCRF).

## 7.3. Blinding

This is an open-label study.

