### 5.4. Scientific Rationale for Study Design

Conducting the study in healthy subjects mitigates the potential confounding effects of the disease state and concomitant medications in patients. Healthy subjects are frequently used in the assessment of bioavailability of both small and large molecules.

Single doses of LY3074828 and the PK sampling timepoints have been selected to generate PK profiles sufficient to fulfill the study objectives. As the primary endpoints of this study are

PK-related and are not subject to bias, it is not considered necessary for this study to be blinded. Subjects and site staff will be aware of the administration route.

A parallel-group design was chosen because a crossover design is impractical for compounds that have long half-lives, such as monoclonal antibodies. Additionally, a crossover study design could confound PK data if subjects develop neutralizing ADAs.

Monoclonal antibody therapy has been associated with hypersensitivity reactions, including injection-site reactions. Follow-up details on injection-site reactions will be collected by the investigative site regarding the severity, duration, type, and timing of the start of the event in relation to the start of study drug administration in order to further characterize these events.

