#### **9.4.6. *Injection-Site Assessments***

Injection-site reactions will be evaluated through the collection and review of TEAEs and through the use of an Injection-Site Reaction Follow-up Form completed by the investigator. Local tolerability at the injection-sites will be examined by evaluation of erythema, induration, categorical pain, pruritus, and edema as indicated in Section 2. For each event, the severity, duration, and timing of the event in relation to the administration of study drug will be recorded. If one or more symptom(s) of an injection-site reaction is reported during the assessment, a single AE for injection-site reaction will be recorded on the AE page of the eCRF.

Pain assessments will help to determine if injection volume (1.0 mL versus 1.5 mL) is a contributing factor. For the lyophilized formulation, injection-site assessments of pain and leakage will be performed for the 2 injections in the lower quadrants of the abdomen (1.0 mL and 1.5 mL injections). For both dose levels of solution formulation in PFSs, injection-site assessments of pain and leakage will be performed for the first injection, which will be administered into a lower quadrant of the abdomen.

Pain measurements will be quantified using a 100-mm validated visual analog scale (VAS). The VAS is a well-validated tool (Williamson and Hoggart 2005) for the assessment of injection-site pain, and is presented as a 10-cm (100-mm) line, anchored by verbal descriptors, usually “no pain” and “worst imaginable pain.” The subject will be asked to rate any pain on a scale of 0 to 100 mm on the line immediately (within 1 minute) following the start of the injection and at time points according to the Schedule of Activities (Section 2).

Injection-site leakage will be assessed using pre-weighed filter paper, blotting the injection-site immediately after the injection to absorb any post-injection leakage and placing the filter paper back on the tared analytical balance in a similar manner as previously described (Ignaut and Fu 2012). The amount of leakage will be calculated by subtracting the pre-weighed filter paper measurement from the post-injection-site blot filter paper measurement. Any bleeding from the injection-site will also be documented.

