GCP	good clinical practice
HIV	human immunodeficiency virus
IB	Investigator's Brochure
ICF	informed consent form
ICH	International Council for Harmonisation
IL-12	interleukin-12
IL-23	interleukin-23
informed consent	A process by which a subject voluntarily confirms his or her willingness to participate in a particular trial, after having been informed of all aspects of the trial that are relevant to the subject's decision to participate. Informed consent is documented by means of a written, signed, and dated informed consent form.
interim analysis	An interim analysis is an analysis of clinical trial data, separated into treatment groups, that is conducted before the final reporting database is created/locked.
investigator	A person responsible for the conduct of the clinical trial at a trial site. If a trial is conducted by a team of individuals at a trial site, the investigator is the responsible leader of the team and may be called the principal investigator.
IRB	institutional review board
IV	intravenous
open-label	A study in which there are no restrictions on knowledge of treatment allocation, therefore the investigator and the study participant are aware of the drug therapy received during the study.
PFS	pre-filled syringe
PK	pharmacokinetic(s)
Q1W	once every week
QTc	corrected QT
SAE	serious adverse event

SC	subcutaneous
screen	The act of determining if an individual meets minimum requirements to become part of a pool of potential candidates for participation in a clinical trial.
SUSARs	suspected unexpected serious adverse reactions
t1/2	half-life associated with the terminal rate constant
TB	tuberculosis
TBL	total bilirubin
TEAE	treatment-emergent adverse event: Any untoward medical occurrence that emerges during a defined treatment period, having been absent pretreatment, or worsens relative to the pretreatment state, and does not necessarily have to have a causal relationship with this treatment.
TE-ADA	treatment-emergent anti-drug antibody
tmax	time to maximum observed drug concentration
ULN	upper limit of normal
VAS	visual analog scale

---

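### Nothing in the open-label plan stops Reference-arm subjects knowing which injection is the 1.5 mL one while they rate its pain, so expectation could inflate the exploratory volume contrast

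*Protocol*

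**What the plan says.** Protocol Section 9.4.6 states the question: "Pain assessments will help to determine if injection volume (1.0 mL versus 1.5 mL) is a contributing factor". In the Reference (lyophilized) arm, the two injections into the lower abdominal quadrants, one of 1.0 mL and one of 1.5 mL, are both assessed for pain. Under Table AMAE.2 in Section 7.1, "The order and location of the first 2 injections will be randomized"; Section 7.2 lists four sequences.

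The outcome is the subject's own rating: "The subject will be asked to rate any pain on a scale of 0 to 100 mm on the line". Section 10.3.6 puts the 0-hour score into a linear fixed-effects model with a treatment effect and reports the 1.5 mL versus 1.0 mL difference with a 90% CI.

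On blinding, the whole of Section 7.3 reads "This is an open-label study". Appendix 1 defines open-label as meaning no restriction on knowledge of allocation, so that "the investigator and the study participant are aware of the drug therapy received during the study". Section 5.4 gives the one justification, that the primary endpoints are "PK-related and are not subject to bias, it is not considered necessary for this study to be blinded", and adds: "Subjects and site staff will be aware of the administration route".

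**The concern.** The reason for leaving the study open-label fits a serum concentration. It does not fit a pain score marked by the subject within a minute of an injection. A subject who knows that the larger injection is being given may expect more pain and rate accordingly.

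Randomising order and side balances position and quadrant. It cannot balance expectation, which stays with the volume whichever injection comes first. The planned difference then estimates a volume effect plus an expectation effect, and the data cannot separate them.

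Masking between arms is impractical, because the arms differ in number of injections and in presentation. Those obstacles are absent for the first two Reference injections. They are the same reconstituted product, given one after the other to the same person with the same type of syringe and needle, both in lower quadrants. At stake is how far the exploratory volume comparison can be believed.

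**Working it through.** **1. The texts side by side.**
- Question: does volume contribute to pain (Section 9.4.6)?
- Outcome: self-rated VAS (Section 9.4.6).
- Contrast: 1.5 mL versus 1.0 mL at 0 hour, Reference arm, 90% CI (Section 10.3.6).
- Protection against order and side effects: randomised (Sections 7.1 and 7.2).
- Protection against knowledge of volume: none in Sections 7.1, 7.2, 7.3, 9.4.6 or the Schedule of Activities.
- Reason for not blinding: PK endpoints only (Section 5.4).

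**2. The plan's own precision figure.** The only one is for PK (Section 10.1): 90% probability that the 90% CI half-length is at most 0.32 on the log scale, with CV 49% and 16 per arm.
- SD(log) = √ln(1 + 0.49²) = 0.4639.
- Expected half-length = t(0.95, 30) × 0.4639 × √(2/16) = 0.2784.
- With 90% assurance: 0.2784 × √(χ²(0.90, 30)/30) = 0.3225, which agrees with 0.32.

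This says nothing about pain. The documents give no VAS SD and no expected difference, so what follows is illustration only.

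**3. Precision of a paired volume contrast.** Inputs: n = 18 (Reference arm as randomised); SD of within-subject differences 10 to 20 mm (assumed). Half-width = t(0.95, 17) × SD/√18:
- SD 10 mm: 4.10 mm
- SD 15 mm: 6.15 mm
- SD 20 mm: 8.20 mm

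**4. The same without a subject term.** Section 10.3.6 names a treatment effect and no subject effect. Taking 18 scores per volume as independent, with an assumed score SD of 10 to 20 mm, half-width = t(0.95, 34) × SD × √(2/18), or about 5.6 to 11.3 mm.

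**5. What a bias would do.** Assume no true volume effect, the paired analysis, and an expectation bias *b* towards the larger injection. The chance that the 90% CI excludes zero comes from the noncentral t distribution with 17 df and noncentrality *b*√18/SD. With no bias it is 0.10.

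| Assumed bias | SD 10 mm | SD 15 mm | SD 20 mm |
|---|---|---|---|
| 3 mm | 0.34 | 0.21 | 0.16 |
| 5 mm | 0.65 | 0.39 | 0.27 |

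With 16 subjects the values are slightly lower: 0.31, 0.20 and 0.16 for 3 mm; 0.60, 0.36 and 0.25 for 5 mm. All are on the untransformed millimetre scale, and both the SD and the bias are assumed.

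**The case against.** **It hardly matters.** VAS pain falls under the exploratory objective in Table AMAE.1. The sample size rests on PK, and no decision rule uses pain. The data review in Section 10.3.7 serves manufacturing and Phase 3 dose selection and does not mention pain. SAP Section 9.4.12 plans no inferential safety or tolerability analysis. All of this stands and limits the point to a minor improvement. It does not remove it: SAP Section 11 reports no change from the protocol analyses, the protocol specifies a model and a CI, and a descriptive difference would carry the same bias. The SAP's own pain text is not readable, so its plan cannot be checked.

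**Subjects may never learn the volume.** A reader might infer that they are told the sequence. The documents do not say so; Section 5.4 mentions only the route. Section 7.1 refers to pharmacy handling instructions that are not available here and could include concealment, and a common syringe type may leave only the fill level as a visual cue. This stands. What can be said is that the readable plan does not prevent such knowledge.

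**The purpose of the randomisation is inferred.** A reader might conclude that order was randomised in order to show that volume causes pain. No sentence says this, and Section 9.4.6 speaks only of a contributing factor. The link is reasonable but is an inference.

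**The numbers are assumed.** Correct. The paired half-width is also not that of the model as written, which is why step 4 is shown; there a 5 mm bias is about 44% to 89% of the half-width.

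**A screen cannot fully mask.** Also correct: a 1.5 mL injection may be recognised by its duration, and staff know the volume.

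**Conclusion.** The point holds as a limited one. For the exploratory 1.5 mL versus 1.0 mL contrast, the open-label statement leaves the subject free to know which injection is larger while self-rating pain. The PK-based rationale does not cover that contrast, and randomised order and side do not remove an expectation tied to volume. Such an expectation could create or inflate an apparent 1.5 mL excess.

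A reader might infer that it could equally hide a volume effect. The mechanism does not support that: raising the rating of the larger injection masks a difference only if the larger injection truly hurts less, and nothing in the documents suggests this. Nor do the documents show that bias will occur, or how large it would be. The half-width of 4.1 to 8.2 mm rests on an assumed SD and a paired analysis that Section 10.3.6 does not name. The PK endpoints and the sample size are untouched. This is a cheap improvement, not a defect that threatens the trial.

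**What to change.** Add to Section 7.3 and the pharmacy instructions: *In the Reference arm, the subject is not told which of the first two injections is 1.5 mL, and the syringes are kept out of the subject's view until both 0-hour VAS scores have been recorded. The study is otherwise open-label.*

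In Section 10.3.6, describe the 0-hour contrast as having volume concealed from the subject where practicable. Do not call it subject-masked, because duration may reveal the volume and staff are aware of it. State residual expectation bias as a limitation, and restrict the description to the 0-hour scores, since later ratings follow the end of concealment.

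If the pharmacy instructions already provide for concealment, one sentence in Section 7.3 saying so is enough. If the sponsor prefers no concealment, Section 10.3.6 should say that the contrast is open to expectation bias and is to be read descriptively.

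The cost is wording in two documents and a simple screen or drape, with no extra staff, visits or procedures and no change to dosing, randomisation or PK sampling. The drawback is that concealment is only partial.
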